7.0 TRIAL PROCEDURES

7.1 Trial Procedures

The Schedule of Assessments -Section 6.0 summarizes the trial procedures to be performed at each visit. Individual trial procedures are described in detail below. It may be necessary to perform these procedures at unscheduled time points if deemed clinically necessary by the investigator.

Furthermore, additional evaluations/testing may be deemed necessary by the Sponsor and/or Merck for reasons related to subject safety. In some cases, such evaluation/testing may be potentially sensitive in nature (e.g. HIV, Hepatitis C, etc.), and thus local regulations may require that additional informed consent be obtained from the subject. In these cases, such evaluations/testing will be performed in accordance with those regulations.

7.1.1 Administrative Procedures

7.1.1.1 Informed Consent

The Investigator must obtain documented consent from each potential subject prior to participating in a clinical trial.

Consent must be documented by the subject's dated signature or by the subject's legally acceptable representative's dated signature on a consent form along with the dated signature of the person conducting the consent discussion.

A copy of the signed and dated consent form should be given to the subject before participation in the trial.

The initial informed consent form, any subsequent revised written informed consent form and any written information provided to the subject must receive the IRB's approval in advance of use. The subject or his/her legally acceptable representative should be informed in a timely manner if new information becomes available that may be relevant to the subject's willingness to continue participation in the trial. The communication of this information will be provided and documented via a revised consent form or addendum to the original consent form that captures the subject's dated signature or by the subject's legally acceptable representative's dated signature if the new information would affect the subject's willingness to continue participation in the study as determined by the IRB.

Specifics about a trial and the trial population will be added to the consent form template at the protocol level.

The informed consent will adhere to IRB requirements, applicable laws and regulations and Sponsor requirements.

7.1.1.2 Inclusion/Exclusion Criteria

All inclusion and exclusion criteria will be reviewed by the investigator or qualified designee to ensure that the subject qualifies for the trial.

7.1.1.3 Medical History

A medical history will be obtained by the investigator or qualified designee during the screening period. Medical history will include all active conditions, and any condition diagnosed within the prior 10 years that are considered to be clinically significant by the Investigator. Details regarding the disease for which the subject has enrolled in this study will be recorded separately and not listed as medical history.

7.1.1.4 Prior and Concomitant Medications Review

7.1.1.4.1 Prior Medications

During the screening period, the investigator or qualified designee will review prior medication use, including any protocol-specified washout requirement, and record prior medication taken by the subject within 28 days before written informed consent. Treatment for the disease for which the subject has enrolled in this study will be recorded separately and not listed as a prior medication.

7.1.1.4.2 Concomitant Medications

The investigator or qualified designee will record medication, if any, taken by the subject during the trial. All medications related to reportable SAEs and events of clinical interest (ECIs) should be recorded as defined in Section 7.2.

7.1.1.5 Disease Details and Treatments

7.1.1.5.1 Disease Details

The investigator or qualified designee will obtain prior and current details regarding disease status.

7.1.1.5.2 Prior Treatment Details

The investigator or qualified designee will review all prior cancer treatments including systemic treatments, radiation and surgeries.

7.1.1.5.3 Subsequent Anti-Cancer Therapy Status

The investigator or qualified designee will review all new anti-neoplastic therapy initiated after the treatment discontinuation. If a subject initiates a new anti-cancer therapy within 30 days after treatment discontinuation, the 30 day Safety Follow-up Visit must occur before the first dose of the new therapy. Once new anti-cancer therapy has been initiated the subject will move into Survival Follow-up.

7.1.1.6 Assignment of Screening and Registration Number

Subjects will be assigned a screening and registration number in sequential order by the Coordinating Center's study coordinator, or for participating sites, the Multicenter Network Administrator, or designee. Additional details of this process can be found in the Study Procedures Manual.

7.1.1.7 Trial Compliance (Medication/Diet/Activity/Other)

Subjects will be given a drug diary (Section 14.4) to record doses of vorinostat and any adverse events he or she may experience. Drug diaries will be collected at the start of the next cycle, or at the time of the next clinic visit, whichever is sooner. Any discrepancies in drug accountability will be clarified with the subject.

7.1.2 Clinical Procedures/Assessments

7.1.2.1 Adverse Event (AE) Monitoring

The investigator or qualified designee will assess each subject to evaluate for potential new or worsening AEs as specified in the Schedule of Assessments and more frequently if clinically indicated. Adverse events will be graded and recorded throughout the study and during the follow-up period according to NCI CTCAE Version 4.0 (reference Section 14.2). Toxicities will be characterized in terms regarding seriousness, causality, toxicity grading, and action taken with regard to trial treatment.

All AEs of unknown etiology associated with pembrolizumab exposure should be evaluated to determine if it is possibly an Event of Clinical Interest (ECI) of a potentially immunologic etiology (termed immune-related adverse events, or irAEs); see the separate package insert regarding the identification, evaluation and management of potential irAEs. Detailed information regarding ECIs can be found in Section 14.5.

Please refer to Section 7.2 for detailed information regarding the assessment and recording of AEs.

7.1.2.2 Full Physical Exam

The investigator or qualified designee will perform a complete physical exam during the screening period. Clinically significant abnormal findings should be recorded as medical history. Full physical exams may also be done by the investigator or qualified designee throughout participation in the trial as clinically indicated and as specified in the Schedule of Assessments (section 6.0.) After the first dose of study intervention, new clinically significant abnormal findings should be recorded as AEs.

Investigators should pay special attention to clinical signs related to previous serious illnesses.

7.1.2.3 Vital Signs

The investigator or qualified designee will take vital signs at screening, prior to the administration of each dose of trial treatment and at treatment discontinuation as specified in the Schedule of Assessments (Section 6.0). Vital signs should include temperature, pulse, respiratory rate, weight and blood pressure. Height will be measured at screening only.

7.1.2.4 Eastern Cooperative Oncology Group (ECOG) Performance Scale

The investigator or qualified designee will assess ECOG status (see Section 14.1) at screening, prior to the administration of each dose of trial treatment and discontinuation of trial treatment as specified in the Schedule of Assessments.

7.1.2.5 Tumor Imaging and Assessment of Disease

Imaging studies (CT and bone scan) will be performed at baseline, before Cycle 3, every 3 cycles thereafter and at treatment discontinuation as described in Section 7.1.4.1 below. CT modalities should be done according to standard of care for the patient's disease. Bone scans should be done at baseline and then only as clinically indicated.

Patients in Cohort C (prostate) will have two PET scans using ⁶⁸Ga-PSMA-11: once at baseline and then at 12 weeks (Cycle 4) Not all patients in Cohort C will have the additional PET scans. This determination will be made by the Principal Investigator.

Participant eligibility will be determined using local assessment (Investigator assessment) based on RECIST 1.1. In addition, images (including via other modalities) that are obtained at an unscheduled time point to determine disease progression, as well as imaging obtained for other reasons, but which demonstrate radiologic progression, should also be used to determine progression.

When the Investigator identifies radiographic progression per RECIST 1.1, efforts should be made to verify radiologic PD. Treatment should continue until PD has been verified. Regardless of whether PD is verified, if the Investigator considers the participant has progressed, but elects to implement irRC, the Investigator will assess for confirmation of progression by irRC at subsequent time points.

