¹⁰ When patients are taken off treatment and at the time of disease progression blood for correlative markers will be also obtained.

¹¹ HgbA1c only required for patients with diabetes mellitus at time of study entry.

¹² Only as clinically indicated (Cohort A and B). Standard of care after initial ⁶⁸Ga-PSMA-11 PET (Cohort C)

¹³ Imaging will be done prior to dosing on C3D1.

¹⁴ The run-in phase will only be done during the Dose Expansion Phase and may be waived at the investigator's discretion.

¹⁵ Window for second biopsy is -3 days not +/- 3 days as is the case for other procedures at this time point. Biopsy should occur approximately 2 hours following the most recent dose of vorinostat on cycle 1 day 14. To ensure that these samples are obtained at the correct time, patients are urged to take their vorinostat dose in the clinic on the day of on-treatment sample collection.

¹⁶ Imaging will be done every 3 cycles beginning cycle 6 throughout treatment.

¹⁷ Applicable to a subset of patients in Cohort C (prostate cancer) only, as determined by the Principal Investigator. The Ga-PSMA-11 PET scan should be completed at 12 weeks (C4D1)

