8.9 Efficacy Analysis

Responses will be tabulated and objective response (CR+PR) via RECIST 1.1 will be summarized with the point estimate and corresponding exact 95% confidence interval. For patients with prostate cancer PSA response ($\geq 50\%$ decline from baseline), PSA progression ($\geq 50\%$ increase from baseline/nadir) and bone lesions progression on ^{68}Ga -PSMA-11 PET or bone scans (≥ 2 lesions from baseline with confirmatory scans 6 weeks later showing ≥ 2 additional lesions) will be reported. Progression free and overall survival will be estimated using standard Kaplan-Meier curves. The median time-to-event for each endpoint will be estimated along with the corresponding 95% confidence interval. Similar descriptive analyses will be performed using irRC criteria. Endpoints such as quantitative characteristics of humoral immune response will be characterized by their mean and corresponding 95% confidence interval. No statistical comparisons are planned. Analyses will be done separately by each expansion cohort. Patients enrolled in the Dose Finding Phase will be excluded when estimating efficacy for the design of a future trial.

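### Cohort C bone progression pools PSMA PET and bone scans although only an investigator-chosen subset has PET, and the plan does not say whether PET-only progression counts for PFS

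*Combined protocol and SAP*

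**What the plan says.** **Who has PET.** Section 7.1.2.5 first gives every Cohort C patient two PSMA PET scans, at baseline and at 12 weeks (labelled Cycle 4). It then restricts this: "Not all patients in Cohort C will have the additional PET scans. This determination will be made by the Principal Investigator". Footnote 17 of the Schedule of Assessments agrees: "Applicable to a subset of patients in Cohort C (prostate cancer) only, as determined by the Principal Investigator". Neither place gives a criterion, a target number or a time for the choice.

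**How bone progression is reported.** Section 8.9 has one definition for Cohort C, read on "PSMA-11 PET or bone scans". It asks for at least 2 lesions beyond baseline, then a confirmatory scan 6 weeks later with at least 2 more. It does not name the confirming modality, require the follow-up modality to match baseline, or give PET its own denominator.

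**When bone scans are done.** Sections 7.1.2.5 and 7.1.2.6.1 put CT and bone scan on a fixed schedule: baseline, ahead of Cycle 3, then at three-cycle intervals. Section 7.1.2.5 also says that bone scans after baseline are done only on clinical indication. Footnote 12 reads "Only as clinically indicated (Cohort A and B). Standard of care after initial" PSMA PET for Cohort C. It is silent on Cohort C patients who have no PET.

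**What counts as progression.** Section 7.1.2.5 says that "imaging obtained for other reasons, but which demonstrate radiologic progression, should also be used to determine progression". Section 8.9 estimates PFS by Kaplan-Meier without defining a PFS event. Section 2.1 ties anti-tumor activity to RECIST 1.1.

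**The concern.** A pooled rate over two modalities has a clear meaning only if every patient had the same chance of being found to progress. Here the chance may differ by modality, and the modality depends on an undocumented choice in an open-label cohort of up to 15. Two cohorts with identical disease could report different bone-progression rates because different numbers of patients, or different patients, had PET.

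No hypothesis test is at risk. What is at stake is the meaning of the estimate. Section 8.4 calls the expansion cohorts critical for planning the next phase, and PFS is named in the primary objective (Section 3.1). If the treatment of PET-only progression is left open, it will be settled after the images have been seen.

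**Working it through.** **Plan's own figures.** The total reproduces: 2 × 3 + 45 = 51 and 2 × 6 + 45 = 57, with up to 15 in Cohort C. The plan gives no detection rate, PET number or expected progression rate, so none can be reproduced.

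**Step 1: can a scheduled PET finding be confirmed on PET?** The definition in 8.9 needs two scans after baseline. PET has one. On scheduled scans alone, no patient can meet the confirmed definition by PET. Unless a PET is added, confirmation must use another modality, with a different baseline.

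**Step 2: when does the on-study PET fall?** With 21-day cycles, day 1 of cycle c is day 1 + 21(c − 1).

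- C3D1 = 1 + 42 = day 43; C4D1 = 1 + 63 = day 64; C6D1 = 1 + 105 = day 106.
- 12 weeks from C1D1 is day 85, which is C5D1. C4D1 is week 9.
- Counted from the start of a two-cycle run-in, C4D1 is week 15 and week 12 is C3D1.
- Confirmation 6 weeks later would fall on day 64 + 42 = 106, or day 85 + 42 = 127.

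So 12 weeks and Cycle 4 are different times on either count.

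**Step 3: dependence on the number chosen.** Let k of 15 have PET, and let q_P and q_B be the probabilities of a reported bone progression with and without PET. The expected rate is [k·q_P + (15 − k)·q_B] / 15. The q values below are assumptions.

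| k | q_B = 10%, q_P = 30% | q_B = q_P = 20% |
|---|---|---|
| 0 | 10.0% | 20% |
| 5 | (1.5 + 1.0)/15 = 16.7% | 20% |
| 10 | (3.0 + 0.5)/15 = 23.3% | 20% |
| 15 | 30.0% | 20% |

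If the modalities detect equally, the choice has no effect.

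**Step 4: dependence on which patients are chosen.** Assume 5 patients with a 60% and 10 with a 10% true probability of progression, and detection of 90% with PET and 50% without. The true rate is (3 + 1)/15 = 26.7%.

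- PET in the 5 high-risk patients: (5 × 0.6 × 0.9 + 10 × 0.1 × 0.5)/15 = 3.2/15 = 21.3%.
- PET in 5 low-risk patients: (5 × 0.6 × 0.5 + 5 × 0.1 × 0.9 + 5 × 0.1 × 0.5)/15 = 2.2/15 = 14.7%.
- PET in all: 3.6/15 = 24.0%. PET in none: 2.0/15 = 13.3%.

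With five PETs in both cases, the choice of patients alone moves the expected rate by 21.3 − 14.7 = 6.6 points, which is 1 patient in 15.

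**Step 5: scale.** Exact 95% intervals are 4.3% to 48.1% for 3/15 and 7.8% to 55.1% for 4/15. Every rate in Steps 3 and 4 lies inside both.

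**The case against.** The strongest reply is that the analysis is descriptive, no comparison is planned, and shifts of this size are hidden by sampling error at n = 15. That is true, and no error rate is affected. But the reported interval covers sampling only. It says nothing about unequal ascertainment.

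Four stronger readings are tempting, and the documents do not support them.

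- **That Cohort C PFS does depend on who was chosen.** No PFS event is defined, Section 2.1 points to RECIST 1.1, and 8.9 lists bone progression as a separate item. The 7.1.2.5 sentence on other imaging concerns unscheduled images and images taken for other reasons. A protocol PET is not the first and only arguably the second. The firm finding is that the plan does not say.
- **That the choice can follow suspected on-study progression.** The PETs are a pair with a baseline scan, so the choice belongs at screening. Selection on prognosis remains possible.
- **That patients without PET have only ad hoc bone scans.** This takes one side of an unreconciled conflict. On the fixed schedule all Cohort C patients have scheduled bone imaging, although a Cycle 4 PET is still an extra look.
- **That PET dates progression 21 to 42 days earlier.** The differences 106 − 85 and 106 − 64 are correct arithmetic from C1D1. But the PET date is ambiguous, and the plan does not say whether progression is dated at the first or the confirming scan. Confirmation would fall on day 106 or 127, at or after the C6D1 imaging.

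It is also fair to object to removing PET from PFS altogether. Inclusion criterion 4 admits patients evaluable by bone scan and/or PET, and some might then have no usable imaging.

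**Conclusion.** The concern holds for bone-lesion progression. One pooled result mixes a modality given to a chosen subset, without a stated rule, with one intended for the whole cohort, and the scheduled PETs cannot supply the required confirmation. The effect on the rate is conditional: it arises only if PET and bone scan detect differently. For PFS the finding is a gap. The status of PET-only progression is undefined, so Cohort C PFS may be affected.

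The size cannot be derived from the documents. The 10% to 30% and 14.7% to 21.3% ranges rest wholly on assumed detection and progression rates and lie within sampling error. The case for acting is that the estimate can be made interpretable at very little cost.

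**What to change.** 1. **Section 8.9, bone progression.** Report by modality: bone scan for all Cohort C patients, and PET only for the PET subset with its own denominator. Compare each follow-up scan with a baseline scan of the same modality. State which modality confirms an on-study PET finding, or report that finding as unconfirmed.
2. **Section 8.9, PFS.** State whether PET-only findings are PFS events. Report Cohort C PFS with and without them, and identify patients evaluable only by PET.
3. **Section 7.1.2.5 and footnote 17.** Fix PET selection at registration by a rule that does not depend on patient status, for example consecutive Cohort C registrations up to a stated number.
4. **Reconcile the schedules.** Sections 7.1.2.5 and 7.1.2.6.1 and footnote 12 must agree on bone-scan timing in Cohort C, including patients without PET. Otherwise the bone-scan result in item 1 keeps unequal ascertainment. Also reconcile 12 weeks with C4D1 and name the origin from which weeks are counted.

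The cost is wording and one extra analysis, with no added patients or scans. The Principal Investigator loses discretion over who has PET, and the PET denominator will be smaller than 15.

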7.1.2.6 Tumor Tissue Collection and Correlative Studies Blood Sampling

7.1.2.6.1 Pharmacodynamic Analysis

All biopsies on this trial are optional for patients. Whenever possible, archival tissue from a tumor lesion will be obtained at screening. If archived tissue is not available, patients will be given the option to consent to a biopsy during the screening phase. Patients will also be given the option to consent to a biopsy on Day 14 of Cycle 1 (window -3 days). The treatment biopsy should occur approximately 2 hours following the most recent dose of vorinostat on cycle 1 day 14. To ensure that these samples are obtained at the correct time, patients are urged to take their vorinostat dose in the clinic on the day of on-treatment sample collection.

Biopsy for tumor tissue collection will only be done on patients who have accessible tumor per institutional guidelines. Missed tissue collection will not be considered a protocol deviation for the purposes of this study, as tissue collection is an exploratory objective for this study.

Biomarker studies on tumor and blood biospecimens will be carried out to help understand the mechanism of action of the pembrolizumab and vorinostat combination. The run-in phase will help to assess the effect of single agents on the potential biomarkers. Results from these correlative studies will help in the identification of potential biomarkers of response to the pembrolizumab plus vorinostat combination, ultimately leading to the development of a patient selection strategy for further clinical investigation. As such, collection of tumor and blood biospecimens at baseline and on study will be of great importance.

The pharmacodynamics of vorinostat and pembrolizumab will be evaluated. Correlative studies will include assessment of immune effects Tregs, MDSCs and other immune cells at defined time points per the study calendar (i.e., baseline, Run-in Phase Cycle -2 Days 1 and 14 [Dose Expansion Phase only], Cycle 1 Day 1 before dosing, Cycle 2 Day 1 before dosing, every other cycle day 1 before dosing thereafter, and at treatment discontinuation).

Imaging studies (CT and bone scan) will be performed at baseline, before Cycle 3, every 3 cycles thereafter and at treatment discontinuation.

Relationships between vorinostat exposure and pharmacodynamic effects (e.g. histone acetylation in peripheral blood mononuclear cells (PBMNCs) and changes in T cell subset population) will be characterized. Samples will be processed, PBMNCs isolated and histone acetylation status determined. Blood samples will be analyzed for immune cell sub populations. CD4+, CD4+/Foxp3, CD8+ cells, NK cells will be quantitated by FACS analysis. Foxp3 gene expression will be evaluated by quantitative RTPCR

Correlative studies on blood samples:

- CD45 cells
- Effector CD4 T cells
- Effector CD8 T cells
- FoxP3+ CD4+ Regulatory T cells (Tregs)
- CD11b+ CD14+ HLA-DR low/neg MDSCs
- Circulating microRNAs
- Chemokines profile (i.e. IL-8, HFG, osteopontin, etc.)

Correlative studies on tumor samples

- T effector cells
- Tregs
- MDSCs
- M1/M2 macrophages

Please refer to the Study Procedures Manual for Sample Collection and Processing and shipping instructions.

7.1.2.6.2 Tumor Samples

Formalin-Fixed Paraffin-Embedded Tissue: Archival tissue samples may be obtained from any time prior to drug dosing from either the original diagnosis or from any subsequent biopsy done prior to start of first drug treatment. Paraffin blocks are preferred, but if unavailable, five (5) 4 micron sections and two (2) to six (6) 10 micron sections from the same tumor block will be requested.

Fresh tumor samples: Pretreatment and On Treatment tumor biopsy samples will be collected from patients who consent and who have accessible tumor per institutional procedures. The biopsy sample will be split into **two** portions: one (1) portion will be placed in *RNAlater*TM and one (1) portion will be placed in 10% formalin solution.

The On Treatment samples will be collected ~2 hours following the most recent dose of vorinostat on cycle 1 day 14 (-3 days). To ensure that these samples are obtained at the correct time, patients are urged to take their vorinostat dose in the clinic on the day of on-treatment sample collection. The time of the vorinostat dose and sample collection must be recorded.

Please refer the Study Procedures Manual for additional processing and shipping instructions.

